Quit is defined based on proposed standards [73] as 7 day point prevalence abstinence and continuous abstinence (<5 cigs since quit date). E-cigarette use will not constitute a relapse but will be monitored and reported. Ratings (Likert items, e.g., timeliness) will be evaluated as % of participants and score range (very low, low, moderate, high, very high), with feasibility determined by 75% of participants rating an item as moderate or higher (Aim 1,3). Average responses for a given factor (e.g., satisfaction) on the User Experiences Questionnaire will be tested similarly, and qualitative analysis of open-ended questions will be used to further evaluate acceptability (Aim 3). Adherence cut-offs (e.g., time spent wearing the smartband) will be 80% (Aim 2). Adherence was high in pilot work (90% of participants answered 80% of smoking notifications[14]).

D.5. Assessments

Participants will be provided links to online surveys at baseline, 21 days, 30 days and 60 days (end of study) to measure smoking and other domains ([Table 1](#)) and to provide study instructions including initial mindfulness training (15 min). All surveys will be hosted on Yale Qualtrics secure survey software (<https://yalesurvey.qualtrics.com>) and optimized for delivery on mobile devices. The baseline survey will be automatically provided to eligible participants upon completing the screening survey and providing informed consent. All following surveys will be automatically emailed to the participant at each time point. For non-completed surveys a reminder text message will be sent at 1 and 2 days, followed by a phone call at 3 days. Demographics and smoking characteristics will be evaluated using standardized PhenX Toolkit protocols. Smoking status will include one-week point prevalence abstinence and continuous abstinence [73], cigarettes per day, and other tobacco use (e.g., e-cigarettes). All are standardized measures with documented psychometrics. In addition, across treatment, ratings are delivered as EMA after each mindfulness exercise and include helpfulness, timeliness, craving and affect. At the end of the study, active participants may be asked to take part in an optional debriefing to provide feedback about their experiences in the study.

Table 1. Assessments.

Instrument Name	Domain assessed	Baseline	Day 21	Day 30	Day 60
Demographics	Demographics	X			
Smoking status [73]	Smoking	X	X	X	X
Time Line Follow Back [74] (since last survey)	Daily smoking	X	X	X	X

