Secondary data analysis: As a secondary aim, we will evaluate change in smoking (cigarettes per day) and abstinence at the end-of-study survey. Abstinence will be measured by: 1) self-reported one week point prevalence abstinence and continuous abstinence (> 5 cigarettes since quit date), 2) automatic smartband smoking monitoring and detection for 7 days prior to the assessment, and, 3) a random subset of individuals (50%) who report one-week point-prevalence abstinence at end-of-study will be shipped carbon monoxide breath monitors (coVita, LLC), or saliva kits (Alere iScreen OFD Cotinine Saliva Test) to confirm abstinence from smoking (<10 ppm or negative saliva test) via video chat with a researcher as previously [4, 5] or by submitting a recorded video via email or text. Abstinence rates will be reported for each measure. These data will be used to provide preliminary evidence about whether smartband-based smoking monitoring can inform measures of abstinence. We will use descriptive statistics to inform future studies. Additionally, all interactions with the app will be automatically tracked and evaluated related to engagement and secondary outcomes.

Missing data: In our recent trial [4, 5], most individuals dropped out upon enrollment. Treatment starters used the app 17 ± 8 out of 22 days and completed ratings (EMA) on 14 ± 9 days. We then had 53% treatment completers –defined as 60% of treatment. Retention to the primary 6mo. survey was 84% despite whether subjects had engaged with treatment. Therefore, we do not anticipate significant missing survey data. We are unable to estimate retention at each step but will measure this. Relevant to our aims, other missing data may include smoking data from not wearing the smartband, or ratings data. Primary analyses will use missing at random (MAR) assumptions but we will also perform sensitivity analyses under reasonable missing not at random (MNAR) [80, 81]. For singly-measured outcomes we will use multiple imputation [82, 83] under MAR (primary) and MNAR (secondary analyses). For longitudinal outcomes, our primary approach will be full-information maximum likelihood under MAR [84]. We will fit pattern mixture longitudinal models to test the effect of deviations from MAR [85]. We will compare retained vs. dropouts on different characteristics to inform the MNAR models.

SECTION II: RESEARCH INVOLVING DRUGS, BIOLOGICS, RADIOTRACERS, PLACEBOS AND DEVICES

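### The secondary analysis prints the continuous-abstinence threshold with the sign reversed (more than 5 cigarettes instead of fewer than 5)

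*Combined protocol and SAP*

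**What the plan says.** The criterion for continuous abstinence appears with a number in three places of the combined protocol and SAP.

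- D.4 Outcomes defines quitting "as 7 day point prevalence abstinence and continuous abstinence (<5 cigs since quit date", that is, fewer than 5 cigarettes.
- The overview of Section 13 (Statistical Considerations) repeats that definition with the same sign.
- The secondary data analysis, later in Section 13, lists as its first abstinence measure "self-reported one week point prevalence abstinence and continuous abstinence (> 5 cigarettes since quit date", that is, more than 5 cigarettes.

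D.5 Assessments names the measure without a threshold: "Smoking status will include one-week point prevalence abstinence and continuous abstinence [73], cigarettes per day, and other tobacco use". It therefore does not settle which sign applies.

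The status of the outcome is clear. The secondary data analysis states: "As a secondary aim, we will evaluate change in smoking (cigarettes per day) and abstinence at the end-of-study survey". It adds "Abstinence rates will be reported for each measure" and "We will use descriptive statistics to inform future studies".

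**The concern.** Section 13 contradicts itself on the definition of an outcome that it commits to report. The version with the reversed sign stands in the paragraph that specifies the abstinence analysis, where someone programming that analysis would naturally look. Followed as written, the rule inverts the measure: those who stayed off cigarettes count as failures and those who went on smoking count as successes.

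The abstinence data also have two further uses. They are to give preliminary evidence on whether smartband monitoring can inform measures of abstinence, and the trial as a whole is to inform a larger randomized efficacy trial. A reversed self-report measure would spoil any comparison of smartband and self-report that uses it. Even if the analyst silently applies the sensible rule, a reader who compares the report with the plan will find two opposite prespecified definitions.

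**Working it through.** The plan gives no expected abstinence rate for this measure, so there is no figure to reproduce. The check compares the statements and follows the logic of each rule.

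**1. The two rules, count by count** (whole cigarettes since the quit date)

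| Cigarettes since quit date | Fewer than 5 (D.4, Section 13 overview) | More than 5 (secondary data analysis) |
|---|---|---|
| 0 to 4 | abstinent | not abstinent |
| exactly 5 | not abstinent | not abstinent |
| 6 or more | not abstinent | abstinent |

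The rules agree only at exactly 5. No count is abstinent under both. This needs no data.

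**2. Can the printed rule describe abstinence?** Section 6 (Subject Population) requires at least 5 cigarettes per day at entry, and D.1 gives a post-quit period of 30 days. A participant who never quits and smokes at the entry minimum has 5 × 30 = 150 cigarettes and meets the printed rule. A participant with 0 cigarettes fails it. The printed sign cannot be intended.

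**3. Is it an artefact of text extraction?** Probably not. The same paragraph prints the carbon monoxide limit (below 10 ppm) with the sign the right way round. The wording also differs from the other two places (cigarettes written out instead of abbreviated, and a space after the sign), which suggests that the phrase was typed separately.

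**4. Size, as an illustration.** Among participants with known counts, let p be the share with fewer than 5 cigarettes and q the share with exactly 5. The documents give neither, so both are assumptions. The intended rule reports p; the printed rule reports 1 − p − q.

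| p | q | Intended rule | Printed rule |
|---|---|---|---|
| 10% | 0% | 10% | 1 − 0.10 − 0 = 90% |
| 10% | 5% | 10% | 1 − 0.10 − 0.05 = 85% |
| 30% | 0% | 30% | 1 − 0.30 − 0 = 70% |
| 30% | 5% | 30% | 1 − 0.30 − 0.05 = 65% |

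**5. If the two criteria are read jointly.** The word joining point prevalence and continuous abstinence could mean that both must be met. The percentages in step 4 then do not apply. The printed rule would count only people who smoked 6 or more cigarettes after the quit date and were abstinent for the final 7 days, and would exclude everyone who never lapsed. The classification is still wrong.

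**6. What is not touched.** Seven-day point prevalence and the 7-day smartband measure do not use the 5-cigarette threshold. Biochemical confirmation is offered to a random 50% of those who report point-prevalence abstinence, so it does not use it either. The 75% rating criterion and the 80% adherence cut-off do not depend on abstinence.

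**The case against.** The strongest reply is that this is a self-evident slip. The definition is stated correctly twice, once in the overview of the same section, and the faulty version is only a restatement in brackets. Nobody would describe people who smoked more than 5 cigarettes as continuously abstinent, so a competent analyst would apply the intended rule. The outcome is secondary and descriptive in a feasibility trial, and no decision rule rests on it. The percentage contrasts show what an implausible reading would produce, from assumed values of p and q.

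Most of this is fair as a statement of scope. The intended meaning can be recovered, and the percentages are illustrations that the point does not need. It does not remove the contradiction, because a prespecified outcome definition should not depend on the analyst noticing that it is reversed. Under the joint reading in step 5, moreover, the resulting rate need not look odd, so the error might not reveal itself.

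A second reply is that the cut-off is taken from a cited proposal for a common outcome standard in cessation trials, and the documents do not show whether that standard counts exactly 5 as abstinent. That is true and cannot be checked here. It bears on the boundary value only, not on the direction of the sign.

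**Conclusion.** The concern holds. The secondary data analysis defines continuous abstinence with the opposite sign to D.4 and the Section 13 overview, and as written it classes no one abstinent whom those two sections class abstinent. That conclusion rests on the text alone.

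The size in percentage points depends on assumed shares, applies to participants with known counts, and requires continuous abstinence to be reported as a measure of its own. The plan's multiple imputation for missing outcomes is not modelled. Within those limits the reported rate would be grossly wrong: 85% to 90% instead of 10%, or 65% to 70% instead of 30%.

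The error should be corrected, but it is narrow. It affects one secondary, self-reported, descriptive measure and leaves the feasibility conclusions untouched.

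**What to change.** In the secondary data analysis of Section 13, change the threshold to fewer than 5 cigarettes since the quit date, as in D.4 and the Section 13 overview, and use identical wording in all three places. Under that rule exactly 5 is already classed as not abstinent, so no further rule is needed. When making the edit, the sponsor may wish to confirm the boundary against the cited outcome standard.

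The cost is a one-character correction before analysis. Design and data collection do not change: Table 1 in D.5 already collects daily smoking since the last survey at day 60, with the quit date set at 30 days.

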This study will test the feasibility of a smartband/smartphone-based smoking detection and brief mindfulness intervention (Fig 1), described in detail below. An initial pilot study will be run using the same approach (N=10). First, smokers will wear a smartband for 21 days to automatically monitor and detect smoking and will be notified of smoking episodes in real time to bring attention to their smoking behavior. Their smoking data from this time will be used to develop individualized smoking profiles. They will be instructed to smoke as much or as little as they like [68] but will set a quit date at 30 days. This timing was chosen to balance motivation to quit with time to collect enough smoking tracking data to predict smoking behavior. All subjects will be encouraged at study onset to utilize quit smoking medications to help cope with nicotine withdrawal, to meet clinical guidelines [71] and as in our prior work [72] by directing them to the medications and nicotine replacement therapy pages of <http://smokefree.gov>. Next, they will be provided with information on how mindfulness could be useful to smokers and will be introduced to the brief mindfulness exercises as part of an online mindfulness training (15 min). The “mindful smoking” exercise will then be triggered by any detected smoking episode for 7 days prior to their quit date, to bring awareness to the present moment effects of smoking. Finally, for 30 days post-quit, the RAIN exercise will be delivered to smokers prior to each predicted smoking episode according to their individualized smoking profile, to help them cope with cravings. They will continue to wear the smartband to monitor for smoking, and any detected smoking episode (i.e., relapse) will trigger the mindful smoking exercise. More generally, smokers can “delay” or “skip” any mindfulness exercise and will be compensated for wearing the smartband as described below. Additionally, the mindfulness exercises will be accessible in their previous text messages for the smoker to use any time they have a craving to smoke. All interactions with the smartband app will be time stamped including onset/offset of mindfulness exercises. This trial will test the feasibility of the intervention including treatment fidelity, adherence and acceptability, to inform a larger randomized controlled efficacy trial.

[figure not shown]

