Participants (N=110: n=10 for the pilot study, n=100 for the feasibility trial): Inclusion criteria: (a) at least 18 years of age; (b) daily smokers (≥ 5 CPD); (c) for at least 2 years; (d) own an Android phone or iPhone; (f) fluent in English as content is only available in English*; and (g) motivated to quit smoking, as indicated by ≥ 18 of 20 on the Action subscale of the Readiness to Change Questionnaire [78] as previously [4, 5]. Exclusion criteria: (a) e-cigarette use (some days/every day) because the smartband technology is not yet able to distinguish e-cigarette use. Recent reports indicate that 10.6% of current cigarette smokers had used e-cigarettes in the past 30 days and 3.6% regularly use e-cigarettes (≥ 20 of the past 30-days) [79]. Therefore, we do not expect dual use to negatively impact recruitment. Other tobacco product use including e-cigarettes will be monitored at each time point (see "Assessments"). No other exclusion criteria. Possible confounds include concurrent use of quit smoking and other psychotropic medications. These will be monitored for confounding effects using our medication use questionnaire.

*Materials will be developed in Spanish during the course of this research, however only English-speaking individuals will be currently enrolled.

7. **Subject classification:** Check off all classifications of subjects that will be specifically recruited for enrollment in the research project. Will subjects who may require additional safeguards or other considerations be enrolled in the study? If so, identify the population of subjects requiring special safeguards and provide a justification for their involvement.

 Children	 Healthy	 Fetal material, placenta, or dead fetus
 Non-English Speaking	 Prisoners	 Economically disadvantaged persons
 Decisionally Impaired	 Employees	 Pregnant women and/or fetuses
 Yale Students	 Females of childbearing potential	

NOTE: Is this research proposal designed to enroll children who are wards of the state as potential subjects?

Yes No

8. **Inclusion/Exclusion Criteria:** What are the criteria used to determine subject inclusion or exclusion?

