- iii. App data: App data is collected, managed and stored according to standardized protocols at Somatix, Inc. Data is collected from the smartphone app to the Somatix backend platform and to the database running over Hypertext Transfer Protocol for secure communication (HTTPS). All data is stored on Amazon Web Services (AWS) - Cloud Computing, Relational Database Service (Amazon RDS) for MySQL, secured using Amazon's advanced capabilities. Any personal-identifying information (e.g., location) will be encrypted in the database. Only authorized Somatix, Inc. personnel will have access to this database. The database will only be accessed by Somatix's password-protected computers. The participant will be identified only by a fake phone number in Somatix database. Somatix will not have access to the key linking a participant's personal information (real phone number) to this fake phone number. Only the fake phone number will be associated with the participant's data in the Somatix database.

(iii) Nicotine withdrawal: Nicotine withdrawal can be uncomfortable but is not life threatening and the risks are minimal compared to the health risks of continued smoking. Subjects will be provided information on how to best tolerate their withdrawal symptoms. Subjects will be encouraged at study initiation to use nicotine replacement therapy and quit smoking medications, by referring them to medications information on <https://smokefree.gov>.

(iv) The involvement of Somatix Inc. does not engage them in human subjects research, therefore human protection training is not required by Yale. To ensure that the company securely maintain the study data, we have obtained the required Security Design Review (SDR) by Yale's Information Security Department and establish a Business Associate Agreement between Yale's HIPAA Privacy Office and Somatix Inc. The SDR process ensures that the security and application of systems are in line with best practices and standards at Yale.

12. **Data and Safety Monitoring Plan:** Include an appropriate Data and Safety Monitoring Plan (DSMP) based on the investigator's risk assessment stated below. (Note: the HIC will make the final determination of the risk to subjects.)

- a. What is the investigator's assessment of the overall risk level for subjects participating in this study?
Minimal risk
- b. If children are involved, what is the investigator's assessment of the overall risk level for the children participating in this study?
NA

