In the unlikely event that such events occur, serious and unanticipated and related adverse events or unanticipated problems involving risks to subjects or others will be reported immediately (if possible), followed by a written report within 7 calendar days of the Principal Investigator becoming aware of the

event to the Yale IRB, Independent Monitoring Monitor(s), and NCCIH. Any other unanticipated problem will be reported to the IRB, Independent Safety Monitor(s), and NCCIH within 14 days of the PI becoming aware of the problem.

To ensure that the design, conduct, and reporting of research for this project is free from bias resulting from Investigator financial conflicts of interest, the project will be conducted in accordance with NIH Financial Conflict of Interest (FCOI) regulation, *Responsibility of Applicants for Promoting Objectivity in Research for which PHS Funding is Sought* (42 CFR Part 50 Subpart F), applicable to grants and cooperative agreements (2011 Revised Regulations) and Yale University Policy on Conflict of Interest.

13. Statistical Considerations: Describe the statistical analyses that support the study design.

Overview: Quit is defined based on proposed standards [73] as 7 day point prevalence abstinence and continuous abstinence (<5 cigs since quit date). E-cigarette use will not constitute a relapse but will be monitored and reported. Ratings (Likert items, e.g., timeliness) will be evaluated as % of participants and score range (very low, low, moderate, high, very high), with feasibility determined by 75% of participants rating an item as moderate or higher. Average responses for a given factor (e.g., satisfaction) on the User Experiences Questionnaire will be tested similarly, and qualitative analysis of open-ended questions will be used to further evaluate acceptability. Adherence cut-offs (e.g., time spent wearing the smartband) will be 80%. Adherence was high in pilot work (90% of participants answered 80% of smoking notifications [14]).

Aim 1. To assess treatment fidelity for a smartband/smartphone-based mindfulness

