All portable devices must contain encryption software, per University Policy 5100. If there is a technical reason a device cannot be encrypted please submit an exception request to the Information Security, Policy and Compliance Office by clicking on url <http://its.yale.edu/egrc> or email [contact]

5. What will be done with the data when the research is completed? Are there plans to destroy the identifiable data? If yes, describe how, by whom and when identifiers will be destroyed. If no, describe how the data and/or identifiers will be secured. *Write here*

Data collected in the study will reside in our electronic storage mechanism for 7 years. All data analyses (deidentified and coded as described above) will be performed under approved HIC protocols.

6. If appropriate, has a Certificate of Confidentiality been obtained?

This project has NIH funding (1R34AT010365-01) and therefore a CoC was automatically issued in accordance with NIH CoC Policy (NOT-OD-17-109).

SECTION V: POTENTIAL BENEFITS

Potential Benefits: Identify any benefits that may be reasonably expected to result from the research, either to the subject(s) or to society at large. (Payment of subjects is not considered a benefit in this context of the risk benefit assessment.)

By participating in this research participants will receive free smoking cessation technology (smartband, smartphone app). By offering free quitting strategies, this study may help to engage more smokers into treatment, thus reducing the enormous health care costs and loss of lives associated with cigarette smoking.

SECTION VI: RESEARCH ALTERNATIVES AND ECONOMIC CONSIDERATIONS

1. **Alternatives:** What other alternatives are available to the study subjects outside of the research? Alternatives to treatment in this study are currently approved over the counter smoking cessation treatments such as the nicotine patch, nicotine gum, and nicotine lozenge. Subjects may get prescriptions from their physicians for varenicline, bupropion, the nicotine nasal spray, or the nicotine inhaler. Subjects will be recommended to use quit smoking medications while participating in this study.

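### A negative saliva cotinine test counts as confirmation of abstinence, but the protocol encourages nicotine replacement, so a true abstainer sent a saliva kit can be wrongly disconfirmed.

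*Combined protocol and SAP*

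**What the plan says.** Section 13, Secondary data analysis, lists three measures of abstinence: self-report, smartband detection over the preceding seven days, and a biochemical check. For the third, a random 50% of those reporting one-week abstinence at the end of the study are sent breath CO monitors "or saliva kits (Alere iScreen OFD Cotinine Saliva Test) to confirm abstinence from smoking (<10 ppm or negative saliva test"). The two tests form one measure. A rate is reported for each measure, and the data are meant to show whether the band can inform the measurement of abstinence.

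On nicotine products, the protocol says:

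- D.1 Overview: "All subjects will be encouraged at study onset to utilize quit smoking medications to help cope with nicotine withdrawal".
- Section 11, Minimizing Risks: "Subjects will be encouraged at study initiation to use nicotine replacement therapy and quit smoking medications".
- Section VI, item 1 (Alternatives): "Subjects will be recommended to use quit smoking medications while participating in this study". The same paragraph names "approved over the counter smoking cessation treatments such as the nicotine patch, nicotine gum, and nicotine lozenge" and, by prescription, "varenicline, bupropion, the nicotine nasal spray, or the nicotine inhaler".
- D.4 Outcomes and the section 13 Overview: "E-cigarette use will not constitute a relapse but will be monitored and reported".
- Section 6: "Exclusion criteria: (a) e-cigarette use (some days/every day"). Section 8 repeats this.

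The day-60 survey includes the medication use questionnaire (Table 1), and smoking status covers other tobacco use (D.5). Section 8 says medication use is monitored as a possible confounder. Nothing ties these answers to the choice or reading of the test.

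**The concern.** The confirmation criterion and the advice to participants work against each other. Cotinine is a metabolite of nicotine, so the saliva test detects nicotine intake, not smoking (general assay knowledge; the kit's cutoff is not given). A participant can follow the study's advice, meet its definition of quit, and still test positive. As written, the criterion has no exception for that person.

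Two results could be distorted. The biochemically confirmed rate could be too low, and because CO and saliva share one measure, a pooled rate would not show why. The band could also be misjudged: an NRT user whom the band correctly records as not smoking, but whose saliva is positive, would look like a smoker the band had missed. If only a saliva kit was shipped, a CO reading from that time cannot be recovered later.

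**Working it through.** The plan states no expected confirmation rate, so there is no figure to reproduce. What follows only bounds the effect.

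**Inputs from the documents**

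- Feasibility sample: 100 (section 6).
- Share of self-reported abstainers tested: 0.5 (section 13).
- Abstinence, borrowed for illustration: 13% from a cited app trial (A.1) and 36% from the group's in-person programme (A.3).

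**Assumptions, since the documents give no values**

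- *u*, share of tested abstainers using a nicotine product: 10%, 30%, 50%.
- *s*, share sent saliva kits, taken as unrelated to nicotine use: 0, 0.5, 1.
- *p*, share of those users who test cotinine-positive: 1 (worst case) or 0.5.
- Every self-reported abstainer is truly abstinent, which makes the head counts upper bounds.

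**Step 1. Number tested** = 100 × abstinence × 0.5. At 13% this is 6.5; at 36% it is 18.

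**Step 2. Share of tested true abstainers wrongly failed** = *u* × *s* × *p*.

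| *u* | *s* = 0 | *s* = 0.5, *p* = 1 | *s* = 0.5, *p* = 0.5 | *s* = 1, *p* = 1 |
|---|---|---|---|---|
| 10% | 0% | 5% | 2.5% | 10% |
| 30% | 0% | 15% | 7.5% | 30% |
| 50% | 0% | 25% | 12.5% | 50% |

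**Step 3. Heads**, at 30% use with half sent saliva kits:

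- *p* = 1: 6.5 × 0.15 = 0.97 and 18 × 0.15 = 2.7.
- *p* = 0.5: 6.5 × 0.075 = 0.49 and 18 × 0.075 = 1.35.

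**Step 4. Effect on a rate.** With 15% wrongly failed, a true 36% would read as 36 × 0.85 = 30.6%, and a true 13% as 13 × 0.85 = 11.1%.

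**Step 5. Comparison with sampling error.** If 15 of 18 are confirmed, the exact 95% interval is 59% to 96%. Chance variation is larger than the bias, but an interval displays it; the bias runs one way and does not show in a pooled rate.

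**Step 6. Can the test be chosen in time?** Kits go out only after abstinence is reported at the end of the study, and the day-60 survey also asks about medication and other tobacco use. The information needed can be in hand before shipping.

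**The case against.** The strongest case against is that exposure at testing is not shown. Participants are pointed to web pages at study onset, no passage says NRT is supplied, and testing comes about 30 days after the quit date. Saliva kits may rarely be used: the equipment-return text in Section VI, item 2 mentions one only if applicable, and the parallel text in D.10 lists only the CO monitor. This stands, and is why the size is left open. It does not remove the conflict, because Section VI, item 1 recommends medication throughout participation and the criterion makes no allowance for it.

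Nicotine use is also already recorded, with a stated intent to look at confounding, so many positives could be explained afterwards. That is partly right, but no written step applies those answers to the test result.

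A reader might infer that e-cigarettes are as important a route as NRT. The documents do not support that. Some-day and every-day users are excluded at entry, so only later uptake matters. Section 6 also says the band cannot yet distinguish e-cigarette use, so a clean contrast between band and cotinine cannot be assumed for vapers.

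Finally, CO has its own weakness. It reflects recent smoking over a window shorter than seven days (general assay knowledge), so moving people to CO trades some false failures for possible false confirmations. And if reported nicotine use alone could excuse a positive, self-report would override the test meant to check it. Both points stand and shape the fix.

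**Conclusion.** The concern holds. Followed as written, the criterion can disconfirm a true abstainer who uses NRT, and no other section repairs it. The direction is downward for the confirmed rate.

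The size is unknown: zero if all selected participants get CO and, under the assumptions above with half sent saliva kits, at most 5–25% of tested true abstainers. At 30% use that is at most about 1 of 6.5 to 2.7 of 18 people.

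A reader might infer that the abstinence findings as a whole are unreliable or that the confirmed rate will be badly understated. The documents support neither. The outcome is secondary and descriptive, self-report and band rates are given separately, and Aims 1–3 do not depend on it. Participants tested by CO, those using no nicotine product, and those on varenicline or bupropion alone are untouched. The case for a change is that the error is avoidable, not that it is large.

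**What to change.** In section 13, Secondary data analysis:

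1. Use the day-60 medication and tobacco-use answers to choose the test. Send the already planned CO monitor to selected participants reporting current nicotine-product use, and use cotinine kits only for those reporting none.
2. Report CO and saliva results separately.
3. If a saliva positive still occurs in someone reporting nicotine use, follow it with a CO test where possible. Otherwise show it as its own category, and give the confirmed rate twice: counting it as not confirmed, and excluding it.

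The cost is small. Under the same assumptions, nicotine users need 6.5 × 0.10 = 0.65 to 18 × 0.50 = 9 monitors in total. That is about 0.3 to 4.5 more than if half would have received CO anyway, and at most 9 more if none would. Monitors are returned (D.10), though the documents do not say how many are available. An occasional follow-up CO test adds a shipment.

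The plan should state two downsides. Allocating by reported nicotine use makes the CO and saliva groups non-comparable, so their rates should not be read as a comparison of tests. And because CO covers less than the seven-day definition, some false confirmations remain possible.
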